## 15. APPENDIX 2: STATISTICAL ANALYSIS CONVENTIONS

### 15.1. CALCULATION OF A DURATION

Duration in years or months (i.e. treatment duration, follow-up time, disease and treatment free intervals, time from diagnosis to study entry, time to first response, duration of response, stabilisation and disease control, PFS and overall survival) will be calculated as follows :

$$\text{Duration (in months)} = \frac{(\text{Date 2} - \text{Date 1}) + 1}{30.4375}$$

with Date 2  $\geq$  Date 1.

$$\text{Duration (in years)} = \frac{(\text{Date 2} - \text{Date 1}) + 1}{365.25}$$

For example, age of the patients will be calculated as follows :

$$\text{Age (in years)} = \frac{(\text{Date of registration} - \text{Date of birth}) + 1}{365.25}$$

### 15.2. CALCULATION OF A DELAY

Delays, usually in days, (i.e. number of days of delay in a cycle, delay between randomisation and first administration, number of days between last administration or visit and death, delay between diagnosis and study entry, delay between diagnosis and progression, time from randomisation to first concomitant radiotherapy) will be calculated as follows :

$$\text{Delay (in days)} = \text{Date 2} - \text{Date 1}$$

with Date 2  $\geq$  Date 1.

### 15.3. MISSING DATA

#### 15.3.1. General conventions

Following internal biometry conventions are used:

- “A” stands for a non-applicable information,
- “M” stands for an information not present on CRF form,
- “D” is indicating that the mention “Not done” was ticked on the page,
- “O” is a code for a date ongoing,
- “K” is an abbreviations for unknown information.

### **15.3.2. Conventions for dates**

For dates, if the day is missing then convention is to put the day to the value of 15 (half of the month). If the day and the month are missing then convention is to put the day to the value of 01 and the month to the value of 07 (half of the year). This convention allows to approximate some delays (mostly delays analysed at baseline).

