## 4.1. PRIMARY EFFICACY PARAMETERS

The primary efficacy parameter is progression-free survival (PFS) according to the investigator. RECIST version 1.1 will be used.

Progression-free survival will be calculated from the date of randomisation until the date of progression or death (whatever the reason of death).

The progression-free survival may be censored at the date of last tumour assessment or the date of last contact of a follow-up showing no progression, whichever occurs last, in the following cases:

- On-going patients
- Lost to Follow-Up
- Consent withdrawn
- New Anti Cancer therapy given
- No post baseline assessment
- Adequate assessment no longer available (i.e. non evaluable tumour)
- No baseline assessment.

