## 5. SAFETY PARAMETERS

### 5.1. ADVERSE EVENTS

Each patient will be assessed for occurrence of adverse events. The CTCAE version 3.0 will be used. Adverse events not classified by the CTCAE will also be reported and graded according to their severity: mild (grade 1), moderate (grade 2), severe (grade 3), life-threatening or disabling (grade 4), sudden death (grade 5), not applicable in case of progression or adverse event not gradable according to CTCAE and leading to dose modification (NA).

Treatment Emergent Adverse Event (TEAE) will be considered for analysis of adverse effects. A TEAE is defined as any event that first occurred during the treatment period (i.e. from first drug administration date up to last administration date + 30 days) or that “worsened” during that study period. The definition of “worsening” is described below:

- Any increase in the grade (according to CTCAE) compared to baseline adverse event,  
or
- Any adverse event becoming serious during the study period, or

- Any adverse event not pre-treated at baseline requiring a corrective treatment during study, or
- Any adverse event requiring a modification of the study drug administration, or
- Any adverse event becoming possibly, probably or definitely related to the study drug

An adverse event that meet one of the criteria described above will be considered as TEAE and reported in the analyses for the reminder of the study, even if the TEAE downgrades to baseline situation.

Baseline situation of the pre-treatment adverse events will be determined by using:

- the worst grade of the adverse event during the pre-study period (within 2 weeks prior to treatment),
- the seriousness of the event during the pre-study period,
- the use of corrective treatment (even if stopped at the day of first administration) during the pre-study period.

This situation will be used as comparator to determine whether an existing adverse event during study period becomes treatment-emergent (i.e. if at least one of these previous parameters gets worst during study treatment).

The adverse events and signs and symptoms will be classified using the Medical Dictionary for Regulatory Activities (MedDRA). The implementation of this international terminology in the Oracle Clinical® database will be performed using the available version of MedDRA. Each description of the toxicity (verbatim) will be associated with the five following items:

- System Organ Class (SOC),
- High Level Group Term (HLGT),

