- High Level Term (HLT),
- Preferred Term (PT),
- Lowest Level Term (LLT).

The matching of the adverse events reported on the CRF pages with the baseline pre-treatment events to determine the qualification for TEAE will be done by using the Lowest Level Term of the MedDRA dictionary and the qualification for TEAE will be implemented by the study statistician on a dataset provided by the data manager and containing all AEs reported on the CRF pages or derived by the study data manager according to CRF completion guidelines.

Two sets of events will be considered:

- all adverse events regardless of relationship to treatment,
- the adverse events that are possibly, probably or definitely related to treatment,
- If the causality is missing, the AE will be considered as related to study treatment

A cycle will be evaluable for non-haematological toxicity if the following criteria are fulfilled:

- At least one drop or one tablet of any treatment was given,
- The toxicity has been assessed by the investigator during the cycle.

A patient will be evaluable for non-haematological toxicity if at least one cycle is evaluable and will be analysed in the treatment arm she was effectively treated.

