#### **15.6.2. Date of progression or death**

The date of progression is the first date where PD is assessed. The date used for PFS calculation will be the date of progression or the date of death. Date of first progression or death can be found:

- In CTA module of the CRF,
- In ETA module of the CRF (in case of assessment during the follow-up, i.e. after the end of the treatment period),
- In DRF module of the CRF in case of death without “objective” progression assessed before.

If for a tumour evaluation, several assessments show a PD at different dates and the global response of the cycle is PD, the minimum of all the dates of assessment of the cycle showing PD (including appearance of new lesions) will be taken into account.

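### SAP 15.3.2 imputes partial dates without bounds, so an on-treatment adverse event can be dated before first dose, and a death before the last progression-free contact or randomisation

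*SAP*

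**What the plan says.** SAP 15.3.2 covers dates in general. It states that "if the day is missing then convention is to put the day to the value of 15 (half of the month". When the month is also missing, the rule is to "put the day to the value of 01 and the month to the value of 07 (half of the year". On purpose, it adds: "This convention allows to approximate some delays (mostly delays analysed at baseline". It exempts no type of date, and no other rule for partial dates appears in the supplied text.

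Three retained analyses depend on dates that this rule could fill in:

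- **Treatment-emergent adverse events (TEAEs), SAP 5.1.** The window runs "from first drug administration date up to last administration date + 30 days". The baseline comparator is "the worst grade of the adverse event during the pre-study period (within 2 weeks prior to treatment". Matching of reported events to pre-treatment events "will be done by using the Lowest Level Term of the MedDRA dictionary".
- **PFS, SAP 4.1 and 15.6.2.** For patients with an event, "The date used for PFS calculation will be the date of progression or the date of death". Patients without one may be "censored at the date of last tumour assessment or the date of last contact of a follow-up showing no progression, whichever occurs last". That last contact sets a censoring date; it is not a lower limit for an event date.
- **Deaths, SAP 11.2.3 and 15.7.3.** The listing separates deaths up to 30 days after last administration from later ones, and the toxic-death definition uses the same 30 days.

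SAP 15.1 and 15.2 require Date 2 ≥ Date 1 for durations and delays. They do not say what to do when an imputed date breaks that condition.

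**The concern.** A mid-month default is reasonable for a baseline interval that runs over months or years. It is less suitable when a date must be placed on one side of a nearby reference date that is known exactly. First dose, randomisation and last progression-free contact are such reference dates, and the rule ignores them.

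Two outputs are at stake. Safety is the only secondary objective kept after amendment PA06, and its main counts are of TEAEs. PFS is the only efficacy output kept, and SAP 10.2 plans no sensitivity analysis that would show an effect of imputed dates. Errors can run both ways: on-treatment events can move before first dose, and pre-dose events can move after it.

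**Working it through.** The documents give no count of partial dates, so there is no plan figure on this point to reproduce. The one design figure, 310 events, is reproduced by the Schoenfeld formula (309 at HR 0.727, 310 at HR 4/5.5) and does not depend on this rule.

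**Inputs.** Day 15 and 1 July (SAP 15.3.2); TEAE window and two-week pre-study period (5.1); PFS event date (15.6.2); PFS in months = (Date 2 − Date 1 + 1)/30.4375 (15.1). The calendar dates below are illustrations.

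**1. Largest shift.**
- Day missing: 31 − 15 = 16 days too early, or 15 − 1 = 14 days too late.
- Day and month missing (365-day year): 183 days too early (183/30.4375 = 6.0 months), or 181 days too late.

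**2. Adverse event, example.** First dose 20 March; true onset 27 March, recorded only as March. The imputed onset is 15 March, 5 days before first dose. The same happens to every day-missing event in the first-dose month when first dose is on day 16 or later.

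**3. Share of on-treatment events moved before first dose.** Assume a 30-day month, with every pair of first-dose day d and onset day (d to 30) equally likely.
- All pairs: sum over d = 1 to 30 of (31 − d) = 465.
- Pairs with d ≥ 16: 15 + 14 + … + 1 = 120.
- Share: 120/465 = 26%.
- Year-only dates on the same assumption, first dose after 1 July: (183 × 184/2)/(365 × 366/2) = 16,836/66,795 = 25%.

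**4. Share of pre-dose events moved to or after first dose.** Assume first-dose day uniform over 30 days and onset uniform over the 14 days before it.
- All pairs: 30 × 14 = 420.
- Moved: d ≤ 15 with onset in the same month, 0 + 1 + … + 14 = 105. Onsets in the previous month are set to the 15th of that month and stay pre-dose.
- Share of the whole window: 105/420 = 25%.
- Share of those in the first-dose month: 105/(105 + 15 × 14) = 105/315 = 33%.

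**5. PFS, example.** Randomised 20 March; last progression-free contact 22 May; died 29 May, day missing.
- True: (70 + 1)/30.4375 = 2.33 months.
- As written, 15 May: (56 + 1)/30.4375 = 1.87 months. The imputed death is 7 days before a contact at which the patient was alive and progression-free.
- Bounded at 22 May: (63 + 1)/30.4375 = 2.10 months.

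**6. PFS, impossible values.**
- Randomised 20 March, died later that March, day missing: (−5 + 1)/30.4375 = −0.13 months.
- Randomised 1 September, death known only to that year: (−62 + 1)/30.4375 = −2.0 months.

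Both break Date 2 ≥ Date 1.

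**The case against.** **TEAE status does not rest on the imputed date alone.** A reader might infer that the event in step 2 necessarily loses TEAE status. The documents do not support that. SAP 5.1 matches reported events to pre-treatment events by MedDRA Lowest Level Term, and Appendix 1 gives pre-treatment events their own table and listing. An event with no match might be kept as emergent whatever its imputed day. An event already recorded as pre-treatment need not become a false TEAE. The worsening criteria (higher grade, becoming serious or related, needing corrective treatment or a change in study drug) may bring back others. This stands as a limit on the consequence. It does not remove the problem: 5.1 still defines the window by dates, the matching text has no rule for partial onset dates, and neither device corrects the onset date.

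**The rule is meant for baseline history.** The remark on purpose points that way, and PFS is listed under durations (15.1), not delays (15.2). But the remark says mostly, which describes use without restricting scope. The delays in 15.2 also include the time from last administration or visit to death, which is not a baseline interval.

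**The effect is small.** A missing day moves a date by at most 16 days, against a 6-week assessment interval. Progression dates come from tumour assessments and are probably rarely partial (an assumption), so PFS is exposed mainly through deaths. PFS is descriptive with no test (SAP 10.1), and adverse event dates are listed individually. All of this stands and limits the weight of the point.

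**Conclusion.** The point holds as a defect in a stated rule. Followed literally, SAP 15.3.2 can give an on-treatment adverse event an onset before first dose, and can give a death (less likely a progression) a date before the last progression-free contact or before randomisation. The second error yields shortened or negative PFS and breaks the SAP's own date-order condition. For adverse events the supported statement is that they may be misclassified, not that they will be.

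The shares of 26% and 25% are conditional on a day-missing date in the relevant period and on the uniform assumptions in steps 3 and 4. Two larger figures are tempting. Half of first-dose days fall on day 16 or later, but reading that as half of events would make a same-month event as likely after a dose on day 30 as after one on day 1. The 33% in step 4 applies only to pre-dose events in the first-dose month, not to the whole 14-day window.

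Because the number of partial dates is unknown, no total can be given; it is probably small. Alpha and power are unaffected. Any effect falls on the TEAE counts, the 30-day death split, the PFS median and the hazard ratio, in a trial of only 112 patients.

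**What to change.** Keep 15.3.2 as the default and add bounds that apply within the recorded month or year:

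- **Adverse event onset.** Use the later of the imputed date and first dose if all three conditions hold: the partial date is compatible with onset on or after first dose, the event is not recorded as a pre-treatment event, and its stop date does not precede first dose. Events recorded as pre-treatment stay pre-treatment.
- **Progression or death.** Use the later of the imputed date and the last date known progression-free (for progression) or alive (for death), never before randomisation and never outside the recorded month or year.

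Two simpler repairs should be avoided. Restricting 15.3.2 to baseline history would remove the only rule for partial concomitant-medication dates, which SAP 6.1 classifies by date against randomisation. Dating progression or death to the day after the last contact can fall outside the recorded month when that contact was on its last day.

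The cost is a few sentences in the SAP and a few lines of code. The downside is that slightly more events will be counted as treatment-emergent. No sample-size figure changes.

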### **15.4. DOSE MODIFICATIONS**

Dose modifications will be determined between two subsequent cycles. Variation will be calculated by comparing actual dose received.

### **15.5. OVERALL RESPONSE OF THE PATIENT**

According to the revised RECIST, no confirmation of the response will be required in this phase III study to qualify the patient as CR or PR.

### **15.6. DATE OF FIRST RESPONSE AND DATE OF PROGRESSION**

#### **15.6.1. Date of first response**

The date of first response is the first date where CR, or PR is assessed. It can be found in the CTA module of the CRF. If for the same tumour evaluation, the assessments where made at different dates, the maximum of all the dates of assessment of the cycle will be taken into account.

#### **15.6.2. Date of progression or death**

The date of progression is the first date where PD is assessed. The date used for PFS calculation will be the date of progression or the date of death. Date of first progression or death can be found:

- In CTA module of the CRF,
- In ETA module of the CRF (in case of assessment during the follow-up, i.e. after the end of the treatment period),
- In DRF module of the CRF in case of death without “objective” progression assessed before.

If for a tumour evaluation, several assessments show a PD at different dates and the global response of the cycle is PD, the minimum of all the dates of assessment of the cycle showing PD (including appearance of new lesions) will be taken into account.

## 15.7. TOXICITY

### 15.7.1. Haematological toxicities

The following units for HGB, WBC, PLT and ANC will be used for the analysis of haematological toxicity :

Parameters	Units
HGB	g/L
WBC	10  /L
PLT	10  /L
ANC	10  /L

If values were expressed in different units in the CRF, the data management department will be in charge of the conversion to SI units.

Calculation of grades will be done using the following boundaries :

Grade	HGB	WBC	PLT	ANC
Grade 0	]200 – 120]	]15 – 4]	]500 – 150]	]10 – 2]
Grade 1	]120 – 100]	]4 – 3]	]150 – 75]	]2 – 1.5]
Grade 2	]100 – 80]	]3 – 2]	]75 – 50]	]1.5 – 1]
Grade 3	]80 – 65]	]2 – 1]	]50 – 25]	]1 – 0.5]
Grade 4	< 65	< 1	< 25	< 0.5

Of note, the study data manager calculates grades of haematological toxicities before database is made available to the study statistician on a read-only basis.

### 15.7.2. Biochemical toxicities

The following units for SGOT/SGPT, bilirubin, alkaline phosphatase and creatinine will be used for the analysis of biochemical toxicity :

Parameters	Units
SGOT/SGPT	IU/l
Bilirubin	µmol/l
Alkaline phosphatase	IU/l
Creatinine	µmol/l

If values were expressed in different units in the CRF, the data management department will be in charge of the conversion to SI units.

Calculation of grades will be done using the following boundaries:

Grade	SGOT/SGPT	Bilirubin	Alkaline phosphate	Creatinine
Grade 0	[LLN – UNL]	[LLN – UNL]	[LLN – UNL]	[LLN – UNL]
Grade 1	]UNL – 2.5 x UNL]	]UNL – 1.5 x UNL]	]UNL – 2.5 x UNL]	]UNL – 1.5 x UNL]
Grade 2	]2.5 – 5 x UNL]	]1.5 – 3 x UNL]	]2.5 – 5 x UNL]	]1.5 – 3 x UNL]
Grade 3	]5 – 20 x UNL]	]3 – 10 x UNL]	]5 – 20 x UNL]	]3 – 6 x UNL]
Grade 4	> 20 x UNL	> 10 x UNL	> 20 x UNL	> 6 x UNL

Of note, the study data manager calculates grades of biochemical toxicities before database is made available to the study statistician on a read-only basis.

For creatinine clearance, the worst values will be analysed according to the following classes: <50ml/mn or ≥50ml/mn.

### 15.7.3. Definition of a toxic death

A toxic death is defined as a death caused by a related adverse event either during the treatment period or in the 30 days following the last administration.

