#### 9.1.1. Overview of the study

The reasons for treatment discontinuation will be reported. Study discontinuation will be described according to the following reasons: adverse event (related or not), death (related or not), progressive disease, lost to follow up, protocol deviation and other reasons.

The patient status (dead, alive, lost to follow-up ) at the cut-off date will be displayed together with each reason of death (progressive disease, adverse event, other).

The number of patients randomised, treated will be presented by treatment group and overall.

Time between randomisation and first administration will be tabulated by treatment arm.

The duration of follow-up is defined as the time elapsed between the date of randomisation and the date of last news or death, death being a censored observation.

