### **11.2.3. Deaths**

The number and percent of patients dead will be tabulated by treatment arm, including number and percent of dead related to AE/SAE, due to progression or other reasons.

A listing of the deaths within 30 days after last administration or more than 30 days after last administration will be provided with the following variables: patient number, cycle number, date of death, reason of death, source of information.

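### SAP 5.1 gives no fatal grade to a non-sudden fatal adverse event outside CTCAE; SAP 11.2.3 should also state how its death table relates to 15.7.3

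*SAP*

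**What the plan says.** SAP 5.1 grades adverse events by CTCAE version 3.0. For the rest it adds: "Adverse events not classified by the CTCAE will also be reported and graded according to their severity". The top of that second scale runs "life-threatening or disabling (grade 4), sudden death (grade 5". A further category, NA, covers progression and events that CTCAE cannot grade and that led to a dose modification.

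The second scale is used. SAP 11.1 analyses the maximum severity grade of non-haematological events outside CTCAE by cycle, patient and arm. Appendix 1 plans six worst-grade tables by SOC and PT: all events and drug-related events, each per patient and per cycle, and all serious and drug-related serious events per patient.

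On deaths, SAP 15.7.3 defines a toxic death as "a death caused by a related adverse event either during the treatment period or in the 30 days following the last administration". SAP 11.2.3 plans a table of deaths by arm, with counts for those related to AE/SAE, due to progression, or due to other reasons. It also plans a listing of "deaths within 30 days after last administration or more than 30 days after last administration".

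**The concern.** Safety is the only secondary objective still analysed, and a fatal event is its most serious result. A scale whose fatal grade requires suddenness has no place for a patient who dies of an event after days or weeks of illness. A slow course does not make the event less fatal, and the tables that show how severe events were could then present it as non-fatal.

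The second matter is one of linkage. SAP 15.7.3 is the plan's only definition of a drug-caused death, but nothing says which output it serves. The nearest candidate is the AE/SAE row in SAP 11.2.3, which leaves open whether related means related to study treatment or simply due to an adverse event. Two programmers could fill that row differently.

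**Working it through.** The plan states no toxic-death count or rate, so there is no figure to reproduce. The check is to follow each rule to the outputs.

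**1. Where a non-sudden fatal event outside CTCAE can go (SAP 5.1).**

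- Grades 1 to 3 (mild, moderate, severe): do not describe a death.
- Grade 4: nearest in severity, but non-fatal.
- Grade 5: worded for sudden death only.
- NA: reserved for progression, or for an event CTCAE cannot grade that led to a dose modification.
- No grade: the event goes to the listing of ungraded events in SAP 11.1.

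None of these records a non-sudden fatal event as fatal.

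**2. Which outputs this affects.** The six worst-grade tables in Appendix 1 and the by-grade TEAE rows in SAP 11.2.1 depend on the grade. The on-treatment deaths row in 11.2.1, the death table in 11.2.3 and the definition in 15.7.3 set no grade condition. The wording can therefore misplace an event in the severity tables but cannot change a count of deaths.

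**3. Where the toxic-death definition goes.** The term appears in the table of contents and in 15.7.3. No analysis in Section 11 and no output title in Appendix 1 uses it. The 30 days can be read in two ways:

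- Attached to the adverse event: a related event that starts on treatment and kills on day 31 is a toxic death.
- Attached to the death: it is not.

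SAP 5.1 dates treatment-emergent events "from first drug administration date up to last administration date + 30 days" and calls that span the treatment period. If 15.7.3 means the same period, its second half adds nothing, so the text does not settle the reading.

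On either reading, if recorded, the death is within the scope of the 11.2.3 table, which states no time limit, and of the listing, which covers both sides of day 30. The Appendix 1 title of that listing includes relationship to treatment, although the variables named in 11.2.3 do not. Only the AE/SAE row could change, and only if 15.7.3 governs it with the window attached to the death.

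**4. Size, by assumption only.**

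- Per patient: 112 randomised 1:1 gives 112 / 2 = 56 per arm, and 1 / 56 = 1.8%. The documents do not give the number treated per arm, which is the safety denominator under SAP 7.4.
- Late related deaths: if a share p of the 112 patients died of a related event more than 30 days after the last dose, the expected number is 112 × p, and the chance of at least one is 1 − (1 − p)^112.

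| Assumed p | Expected deaths | Chance of at least one |
|---|---|---|
| 0.5% | 0.56 | 43% |
| 1% | 1.12 | 68% |
| 2% | 2.24 | 90% |
| 3% | 3.36 | 97% |

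The table sizes only how many deaths could lose the toxic-death label under the death-dated reading. It does not count deaths missing from the report.

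**The case against.** A reader might infer that the two rules together undercount fatal toxicity: one by cutting off at 30 days, the other by withholding grade 5. The documents do not support this. No toxic-death count is planned under that name, later deaths are tabulated and listed, and no count of deaths depends on grade. SAP 5.1 also treats missing causality as related, which works against undercounting.

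The 30-day window has a sound rationale as well. It matches the TEAE window and the end-of-treatment point. After amendment PA06 the protocol performs no follow-up assessments, and longer follow-up exists only for patients who discontinued before it (Protocol, End of study, and Table 1 notes f and g). A count of deaths at any date would rest on uneven follow-up across patients. The window is not an error in itself.

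On grade 5, the fair reply is that the scale covers only events outside CTCAE, that most people would apply grade 5 to any fatal event, and that ungraded events are listed. The first part stands and limits the point. The second relies on people departing from the written rule. The third does not repair the worst-grade tables and would not catch an event coded as grade 4.

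**Conclusion.** One wording defect stands: as written, the grade 5 entry in SAP 5.1 leaves a fatal but non-sudden event outside CTCAE without a fatal grade, so the worst-grade tables can show it as grade 4, NA or ungraded. It is narrow, and whether any such event occurred is unknown. One event would be 1.8% of an arm if about 56 patients per arm were treated, which is an illustration and not an estimate.

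The link between SAP 15.7.3 and the AE/SAE row of 11.2.3 is unstated and should be clarified. This is minor: a late related death might move out of that row but would remain in the table and the listing. That toxic deaths are undercounted is not shown.

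**What to change.** - **SAP 5.1:** word grade 5 on the scale for events outside CTCAE as *death due to the adverse event*, dropping the condition that it be sudden.
- **SAP 11.2.3:** state whether the AE/SAE row means treatment-related events, and whether 15.7.3 governs it. Name relationship to treatment among the listing variables, as the Appendix 1 title already does.
- **SAP 15.7.3:** if it governs that row, date the window by onset of the event, consistent with the TEAE rule, and keep the existing split at 30 days so that deaths known only through the longer pre-PA06 follow-up stay visible. If it governs nothing, delete it.

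The cost is a few phrases and no new data. Any fatal event outside CTCAE that is already graded should be checked against the new wording. If the onset rule is adopted, a note should say that deaths after the end-of-treatment point were followed systematically only in patients who discontinued before PA06.
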